5.5.11 Labelling

For **BLINDED (olaparib or placebo) THERAPY**, each bottle will be labeled with:

- the protocol number (i.e., "NSABP-B-55")
- the bottle number (i.e., "Bottle 1 of 2, 2 of 2")
- the number of tablets (i.e., "32 tablets")
- the patient ID number (e.g., "E999999", where "E999999" represents a unique patient identifier assigned by NRG Oncology at registration)
- the patient initials (i.e., last initial, first initial, middle initial [e.g., "L, FM"])
- the agent identification (i.e., "Olaparib 150 mg or Placebo")
- a blank line for the pharmacist to enter the patient's name
- administration instructions (i.e., "Take 1 tablet by mouth twice a day. Discard contents after 90 days")
- storage instructions (i.e., "Store below 30°C (86°F).")
- emergency contact instructions
- a Julian date

The Julian date indicates the day the bottle was labeled and shipped and is composed of the last two digits of the calendar year (e.g., 2013 = 13, 2014 = 14) and a day count (e.g., January 1 = 001, December 31 = 365). For example, a bottle labeled and shipped on January 1, 2013, would have a Julian date of '13001' and a bottle labeled and shipped on December 31, 2014, would have a Julian date of '14365'. The Julian date will be used by PMB for recalls. When a lot expires,

PMB will determine the last date the expired lot was shipped and will recall all bottles (i.e., both Olaparib and Placebo) shipped on or before that date thus eliminating any chance of breaking the blind. The combination Julian Date – Order Number, located in the in the upper right hand corner of the bottle label, should be recorded in the lot number field on the Oral DARF.

Each **BLINDED (olaparib or placebo) KIT BOX** will be labeled with:

- the protocol number (i.e., "NSABP-B-55")
- the patient ID number (e.g., "E999999", where "E999999" represents a unique patient identifier assigned by NRG Oncology at registration)
- the patient initials (i.e., last initial, first initial, middle initial [e.g., "L, FM"])
- the agent identification (i.e., "Olaparib 300 mg or Placebo Kit")
- a blank line for the pharmacist to enter the patient's name
- administration instructions (i.e., "Take 1 tablet from each bottle twice a day.")
- storage instructions (i.e., "Store below 30°C (86°F).")
- emergency contact instructions
- a Julian date

5.5.12 Management of toxicity of study treatment

General instructions

- The CTCAE v4.0 must be used to grade the severity of AEs.
- All dose modifications should be based on the AE requiring the greatest modification.
- Therapy should be held until the AE returns to \leq grade 1 unless specified otherwise in the dose modification instructions.
- ***If study drug must be held for more than 4 weeks due to an AE or for any other reasons, permanently discontinue olaparib/placebo.***
- Once a dose has been reduced, dose escalation is not permitted.
- If olaparib/placebo must be permanently discontinued, patient follow-up continues to be required as described on [Table 2](#) and [Table 3](#).
- If any investigational treatment is administered, olaparib/placebo must be discontinued.

5.5.12.1 Study therapy following breast cancer recurrence or second primary cancer

Olaparib/placebo must be discontinued following diagnosis of breast cancer recurrence or diagnosis of a second primary malignancy (i.e., excluding new in situ carcinomas of any site and squamous or basal cell skin cancers). Further therapy is at the investigator's discretion.

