5.5.12.7 Interruptions for intercurrent non-toxicity related events

Study treatment dose interruption for conditions other than toxicity resolution should be kept as short as possible. If a patient cannot restart study treatment within 4 weeks for resolution of intercurrent conditions not related to disease recurrence or toxicity, the case should be discussed with the Protocol Officer (see [Section 13.1](#)). All dose reductions and interruptions (including any missed doses), and the reasons for the reductions/interruptions are to be recorded according to the eCRF guidelines. Study treatment should be stopped at least 3 days prior to planned surgery. After surgery study treatment can be restarted when the wound has healed. No stoppage of study treatment is required for any needle biopsy procedure. Study treatment should be discontinued for a minimum of 3 days before a patient undergoes radiation treatment. Study treatment should be restarted within 4 weeks as long as any bone marrow toxicity has recovered. Because the AEs related to olaparib may include asthenia, fatigue and dizziness, patients should be advised to use caution while driving or using machinery if these symptoms occur.

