5.8 Discontinuation of study treatment

Patients may be discontinued from the study treatment in the following situations:

- Patient decision. The patient is free at any time to discontinue study treatment, without prejudice to further clinical care
- Adverse Event

- Completion of 12 months treatment period
- Confirmed pregnancy during treatment
- Severe non-compliance with study protocol
- Loco-regional breast cancer recurrence (ipsilateral invasive breast cancer recurrence, regional invasive breast cancer recurrence)
- Distant breast cancer recurrence
- Contralateral invasive breast cancer or second primary non-breast invasive cancer
- Death
- Bone marrow findings consistent with myelodysplastic syndrome (MDS)/acute myeloid leukaemia (AML)

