The development of a new primary cancer (second malignancy) should be reported as a SAE. New primary cancers are those that are not the primary reason for the administration of the study treatment and have developed after the inclusion of the patient into the study. They do not include metastases of the original cancer. Symptoms of metastasis or the metastasis itself should not be reported as an AE/SAE, as they are considered to be disease recurrence. New primary cancers are considered as IDFS events and must also be reported on the endpoint CRF. Patients with new primary cancers that can be adequately treated with surgery only and which do not require any additional (neo)adjuvant treatment of any kind can continue to receive investigational product and be followed for secondary endpoints. Rules regarding temporary interruption due to surgery apply (see [Section 5.5.12.7](#)). Patients with new primary cancers which require (neo)adjuvant treatment of any kind for appropriate management must be discontinued from study treatment.

Deaths

All deaths that occur during the study (see [Section 6.4.9](#)) must be reported as follows:

- Death that is clearly the result of breast cancer recurrence or progression should be reported in the DEATH eCRF but should not be reported as an SAE
- Where death that occur within 30 days of the last dose of study treatment is not due (or not clearly due) to breast cancer recurrence or progression of the disease under study, the cause of death must be reported via CTEP-AERS as a SAE within 24 hours (see [Section 6.4.10](#) for further details). The report should contain a comment regarding the co-involvement of progression of disease, if appropriate, and should assign main and contributory causes of death. This information should be captured in the relevant eCRF.

- Deaths with an unknown cause that occur within 30 days of the last dose of study treatment must be reported via CTEP-AERS. A post mortem maybe helpful in the assessment of the cause of death, and if performed a copy of the post-mortem results should be forwarded to the NRG Oncology SDMC within the usual timeframes.
- A copy of the death certificate should be forwarded to the NRG Oncology SDMC if it is readily available or if it contains important cause-of-death information that is not documented elsewhere.
- Please submit the last clinical/office note made before the death or the investigator's note summarizing events resulting in death.

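### Section 6.4.9 permits study treatment to continue after some second primary cancers for which section 5.5.12.1 orders it stopped; the two rules for holds over 4 weeks are also unreconciled.

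*Protocol*

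**What the plan says.** **Second primary cancers.** Section 5.5.12.1 states: "Olaparib/placebo must be discontinued following diagnosis of breast cancer recurrence or diagnosis of a second primary malignancy". Its only carve-out is a parenthesis: "excluding new in situ carcinomas of any site and squamous or basal cell skin cancers".

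Section 6.4.9, under new primary cancers, sets out two branches. Patients whose new cancer can be treated adequately with surgery alone, and "which do not require any additional (neo)adjuvant treatment of any kind can continue to receive investigational product and be followed for secondary endpoints", form the first; the surgical interruption rules of section 5.5.12.7 apply to them. The second is an order: "Patients with new primary cancers which require (neo)adjuvant treatment of any kind for appropriate management must be discontinued from study treatment". The same paragraph says that new primary cancers count as IDFS events.

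Section 5.8.1 says that patients who meet the IDFS endpoint while on study therapy should attend the treatment discontinuation visit and the 30-day follow-up visit.

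**Holds over 4 weeks.** The general instructions in section 5.5.12 read: "If study drug must be held for more than 4 weeks due to an AE or for any other reasons, permanently discontinue olaparib/placebo". Section 5.5.12.7 covers patients who cannot restart within 4 weeks because of an intercurrent condition unrelated to recurrence or toxicity. For them it says that "the case should be discussed with the Protocol Officer". It does not refer back to section 5.5.12.

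**The concern.** A site facing a surgically cured invasive second primary during the treatment year finds an order to stop in one section and permission to continue in another. Nothing in the protocol says which prevails. With about 700 centres planned, the answer may depend on which section was read.

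Two things follow. The first is safety: new second primary malignancy is listed in section 6.4.9 as an olaparib adverse event of special interest, so whether blinded exposure continues after one should not be left to chance. The second is data. Under section 5.8.1, once treatment stops early and the 30-day visit is done, collection of vital signs, laboratory results, routine adverse events and concomitant medications is no longer required. Two identical patients can therefore have different exposure and different routine safety records.

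**Working it through.** The check is mainly a comparison of texts; the only arithmetic is the size.

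**1. Do the exemptions in 5.5.12.1 remove the conflict?** Section 5.5.12.1 exempts in situ carcinomas and squamous or basal cell skin cancers. Section 11.1.1 excludes the same lesions from IDFS events. Section 6.4.9 describes the cancers it is dealing with as IDFS events. Its permission to continue therefore reaches invasive cancers outside the exemption, and the conflict remains.

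**2. Test case, second primary.** Take an invasive second primary diagnosed on treatment, not a squamous or basal cell skin cancer, treated by surgery alone.

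| Section | Consequence |
|---|---|
| 5.5.12.1 | study treatment must stop |
| 6.4.9 | study treatment can continue |
| 5.8.1 | IDFS event on treatment, so attend the treatment discontinuation visit |

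The permission in 6.4.9 is not a stray phrase: it has an opposite branch and its own cross-reference to 5.5.12.7.

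**3. Test case, hold over 4 weeks.** Take a non-toxicity intercurrent condition that prevents restart within 4 weeks. Section 5.5.12 requires permanent discontinuation, since its wording covers any reason. Section 5.5.12.7 requires a discussion and does not say whether resumption is a possible result. The two problems can meet in one patient: 6.4.9 sends surgery-only patients to 5.5.12.7, where treatment may restart once the wound has healed, and healing may take longer than 4 weeks.

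**4. Size of the second-primary conflict.** The only rate in the document is in section 1.4, for new primaries other than MDS/AML:

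- Olaparib-treated patients: 22 / 3862 = 0.57%. Applied to 1800: 1800 × 22 / 3862 = 10.3.
- Adding the 3 blinded cases: 25 / 3862 = 0.65%. Applied to 1800: 1800 × 25 / 3862 = 11.7.

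This gives about 10 to 12 patients. It is a rough guide, because the programme mixes tumour types and treatment durations and its rate is here applied to both arms.

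The affected subset is smaller. Of the 25 patients, 5 + 8 = 13 had up to 12 months of treatment and 2 + 3 + 7 = 12 had longer, beyond this trial's maximum. Using only the 13: 13 / 3862 = 0.34%, or 1800 × 13 / 3862 = 6.1 patients. The programme cases also include basal and squamous cell cancers, which 5.5.12.1 exempts, and haematological cancers, which are not evidently managed by surgery alone. Four of the 25 were reported after olaparib was discontinued.

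No rate is given for non-toxicity holds over 4 weeks, so that conflict cannot be sized.

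**5. Reach into the analyses.** A second primary invasive cancer is already an IDFS event (section 11.1.1), so what happens to treatment afterwards cannot change that patient's IDFS time. The ITT comparison in section 12.1.1 follows randomised treatment regardless of treatment received. Later exposure could bear on OS, and on DDFS after contralateral breast cancer, which section 11.1.2.2 does not count as a DDFS event; with so few patients the effect would be small. A hold over 4 weeks can change exposure before any event.

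**The case against.** The strongest reply is that in each pair only one side is an order. Sections 5.5.12.1 and 5.5.12 command; the surgery-only sentence of 6.4.9 permits, and 5.5.12.7 asks for a discussion. A site that always stops treatment breaches neither of the latter. That is correct, and it means that the texts are not two mandatory rules that cannot both be obeyed. The defect is narrower: a site relying on an express permission in 6.4.9 would breach 5.5.12.1.

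On the 4-week rule, the discussion could end in discontinuation, and 5.5.12.7's own sentence on radiation, with restart within 4 weeks, agrees with 5.5.12. This makes the second conflict softer. It does not dispose of it, because the purpose of the discussion is undefined if discontinuation is already required.

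A reader might infer a third contradictory rule from section 5.8, which begins "Patients may be discontinued from the study treatment in the following situations" and lists second primary cancers. That does not hold. The same list contains death, completion of the 12 months and confirmed pregnancy, and section 6.4.15.1 requires immediate discontinuation for a positive pregnancy test. The list gives reasons for stopping; it does not grant an option to carry on.

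The effect on safety data is also limited. MDS/AML, second primaries and pneumonitis are reported throughout follow-up whatever their timing relative to treatment (sections 6.4.8.2 and 6.4.9). Only exposure and routine adverse event collection depend on the stop date.

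**Conclusion.** The protocol is wrong as written on second primary cancers: 6.4.9 permits what 5.5.12.1 forbids for a non-exempt invasive second primary treated by surgery alone, and 5.8.1 adds to the conflict by sending on-treatment IDFS events to the discontinuation visit. The 4-week conflict is real but weaker. Sites may treat identical patients differently; the document does not show that they will.

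The second-primary conflict probably affects few patients, fewer than the 10 to 12 of 1800 implied by the programme rate for all new primaries other than MDS/AML, on the assumption that this rate carries over to the trial. A reader might assume 1-2%, or 18 to 36 patients, but that exceeds the protocol's own rate and would count cancers that are exempt, off treatment or not managed by surgery alone. Nor does the text support a threat to the primary result: these patients' IDFS times and the validity of the ITT comparison are unaffected. The case for correction rests on patient safety and consistent conduct, not on type I error or power.

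**What to change.** The clinical team should reconcile sections 5.5.12.1, 5.8.1 and 6.4.9 into one rule for second primary cancers, and sections 5.5.12 and 5.5.12.7 into one rule for holds over 4 weeks, including what the Protocol Officer discussion can decide. State each rule once and replace the other statements with cross-references. Which version is right is a clinical decision on which no view is offered here.

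The cost is a short amendment or clarification letter; no new data and no additional patients are needed. Because a parallel version covers patients outside the US, the corresponding text there should be checked at the same time.

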5.5.12.2 Olaparib/placebo dose levels

All olaparib/placebo dose reductions are based on the dose levels listed in [Table 6](#).

Any toxicity observed during the course of the study should be managed by guidelines as outlined in [Table 7](#) [Table 8](#) and [Table 9](#). Once a dose has been reduced, dose re-escalation to a higher dose is not permitted.

Table 6 Olaparib/placebo dose levels

	Dose Level (mg) twice daily				
	Starting Dose	Dose levels for AEs (no re-escalation)		Temporary dose levels due to CYP3A inhibitor exposure	
Olaparib/placebo	300	250	200	150	100

Table 7 Mandatory treatment for hematologic toxicity and treatment guidance for other olaparib/placebo toxicities

Important table instructions:			

 Dose modifications must be based on the AE requiring the greatest modification. 			
	Adverse Event	CTCAE (v 4.0) Grade	Action to be Taken
Hematologic Toxicity Mandatory	Anaemia	2 (8.0-9.5 g/dL)	Hold study therapy until > 9.5 g/dL: If recovery without packed red blood cells transfusion takes: 1-2 weeks – maintain dose; 3-4 weeks – ↓ one dose level If packed red blood cells transfusion given: reduce one dose level
		3, 4	Hold study therapy until > 9.5 g/dL: 1 st appearance – ↓ 1 dose level 2 nd appearance – ↓ 2 dose levels or discontinuation
	Neutrophil count decreased (incl. febrile neutropenia)	3	Hold study therapy until $\geq 1200/mm^3$ ↓ one dose level
		4	Hold study therapy until $\geq 1200/mm^3$ ↓ two dose levels
	Platelet count decreased	2	Hold study therapy until $\geq 75,000/mm^3$ ↓ one dose level
		3,4	Hold study therapy until $\geq 75,000/mm^3$ ↓ two dose levels
Other toxicity deemed to be attributable to study treatment Guidance	Diarrhea (if attributable to olaparib/placebo)	2	Maintain dose or ↓ one dose level
		3	↓ one dose level
		4	Discontinuation
	Mucositis – oral	2	Maintain dose or ↓ one dose level
		3	↓ one dose level
		4	Discontinuation

Table 7 Mandatory treatment for hematologic toxicity and treatment guidance for other olaparib/placebo toxicities

Important table instructions:			

 Dose modifications must be based on the AE requiring the greatest modification. 			
	Adverse Event	CTCAE (v 4.0) Grade	Action to be Taken
Other toxicity deemed to be attributable to study treatment Guidance	Nausea (despite antiemetics)	2	Maintain dose or ↓ one dose level
		3	↓ one dose level
	Vomiting (despite antiemetics)	2	Maintain dose or ↓ one dose level
		3	↓ one dose level
		4	↓ one dose level or discontinuation
	Infection	3	Hold study therapy: When resolved: Maintain dose or ↓ one dose level Repeat appearance – ↓ one dose level
		4	Hold study therapy: When resolved: ↓ two dose levels or discontinuation
	Dyspnea	1, 2, 3	Hold study therapy; rule out pneumonitis Follow instructions in footnote a
		4	Discontinuation
	Pneumonitis	2	Follow instructions in footnote a
		3, 4	Discontinuation
	Other clinically significant AEs deemed related to study treatment ^{b}	2	Maintain dose or ↓ one dose level
		3	↓ one dose level
		4	↓ two dose levels or discontinuation

^a Hold olaparib/placebo and determine etiology. Unless prohibited based on instructions for other clinical diagnoses (i.e. other AEs), resume olaparib/placebo when grade 0 (if the AE requiring olaparib to be held was dyspnea) or when ≤ grade 1 (if the AE requiring olaparib/placebo to be held was ≥ grade 2).

^b Determination of "clinically significant" AEs is at the investigator's discretion.

Table 8 Dose reduction for study treatment to manage moderate renal impairment

Initial dose	Moderate renal impairment (calculated creatinine clearance by Cockcroft -Gault equation or based on a 24 hour urine test between 31 and 50 ml/min): Dose reduction
300 mg twice daily	200 mg twice daily

Table 9 Dose reduction for study treatment with concurrent use of a strong or moderate CYP3A inhibitor

Initial dose	Strong CYP3A inhibitor	Moderate CYP3A inhibitor
300 mg twice daily	100 mg twice daily	150 mg twice daily

For guidance on dose reductions for management of renal impairment refer to [Section 5.5.12.3](#),

For guidance on dose reductions when concomitant strong or moderate CYP3A inhibitors cannot be avoided see [section 5.6.2](#).

5.5.12.3 Renal impairment

If subsequent to study entry and while still on study therapy, a patient's estimated creatinine clearance falls below the threshold for study inclusion (>51 ml/min), retesting should be performed promptly.

A dose reduction is recommended for patients who develop moderate renal impairment (calculated creatinine clearance by Cockcroft-Gault equation or based on a 24 hour urine test of between 31 and 50 ml/min) for any reason during the course of the study: the dose of study treatment should be reduced to 200 mg b.i.d.

Because the creatinine clearance determination is only an estimate of renal function, in instances where the creatinine clearance falls between 31 and 50 mL/min, the investigator should use his or her discretion in determining whether a dose change or discontinuation of therapy is warranted.

Olaparib has not been studied in patients with severe renal impairment (creatinine clearance <30 ml/min) or end-stage renal disease; if patients develop severe impairment or end stage disease is it recommended that study treatment be discontinued.

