Vital signs	X b		X	X (weeks 12 and 24 only)	X	X	X
Haematology / clinical chemistry c	X b,c	X	X	X	X	X	X
Recurrent/new cancers assessment (includes physical exam d, clinical signs and symptoms)	X			X (weeks 12 and 24 only)	X	X	X
Mammogram and/or breast MRI (ipsilateral and/or contralateral) (MRI preferred for patients younger than 50 years) e				X (week 24 only)			
Adverse Events	X	X	X	X	X	X	X

Table 2 Study Schedule – On treatment (Year 1)

Visit Number	2	3	4	5-9 (Every 4 weeks)	10-11 (Every 3 months (14 weeks))	Premature study treatment discontinuation g	Follow-up 30 days after last dose of study medication (all patients)
Week	0	2	4	8, 12, 16, 20, 24	38, 52		
Day	1	15	29				
Visit Window		±3d	±3d	±1 week	±2 week	+2 week	+2 week
Concomitant medications including blood transfusions	X	X	X	X	X	X	X
Demographics j	X						
EORTC QLQ-C30				X (week 24 only)	X (week 52 only)		
FACIT-Fatigue				X (week 24 only)	X (week 52 only)		
Biomarker Blood 2 samples (mandatory)	X i						X
PGx Blood sample (optional)	X						
Blood sample for PK analysis (optional; after signing PK Informed consent) (subset of patients) h			X				
Blood biomarker samples at disease recurrence (Mandatory)	X	X	X	X	X	X	X
Tumour biopsy at disease recurrence (Optional) k	X	X	X	X	X	X	X
Olaparib dispensed/returned f	X		X	X	X	X	

- a Pregnancy tests on serum or urine samples will be performed for women of childbearing potential within 28 days prior to randomisation, on Day 1 of the study prior to commencing treatment, at the time points shown in [Table 2](#) during study treatment and at the 30 day follow up visit. If results are positive the patient is ineligible/must be discontinued from study treatment immediately. Details of the pregnancy tests must be recorded in the patient's medical records and in the CRF.
- b If assessed within 7 days before randomisation, it does not need to be repeated on Day 1 of study treatment unless investigator believes that it is likely to have changed significantly.
- c Safety blood samples do not need to be repeated on Day 1 of study treatment if they have been assessed within 7 days before randomisation and which must have been done at least 3 weeks after the last dose of chemotherapy, unless the investigator believes that they are likely to have changed significantly. Safety bloods samples are to be collected every 2 weeks during the first 4 weeks, then every 4 weeks until week 24 and then at weeks 38 and 52 of study treatment.

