7. Completed at least 6 cycles of neoadjuvant or adjuvant chemotherapy containing anthracyclines, taxanes or the combination of both. Prior platinum as potentially curative treatment for prior cancer (e.g. ovarian) or as adjuvant or neoadjuvant treatment for breast cancer is allowed. (For neoadjuvant patients all chemotherapy should be delivered prior to surgery. No further cycles of chemotherapy post-surgery are allowed.)

8. Patients must have adequate organ and bone marrow function measured within 28 days prior to randomisation with no blood transfusions (packed red blood cells and/or platelet transfusions) in the past 28 days prior to testing for organ and bone marrow function as defined below:

- Haemoglobin ≥ 10.0 g/dL
- Absolute neutrophil count (ANC) $\geq 1.5 \times 10^9/L$

- Platelet count $\geq 100 \times 10^9/L$
- Total Bilirubin \leq ULN (institutional upper limit of normal) except elevated total bilirubin $< 1.5 \times$ ULN due to Gilbert's disease or similar syndrome involving slow conjugation of bilirubin
- AST (SGOT)/ALT (SGPT) $\leq 2.5 \times$ ULN
- ALP $\leq 2.5 \times$ ULN

To rule out metastatic breast cancer, patients with screening ALT/AST or ALP above institutional upper limit of normal should have liver ultrasound, CT or MRI at any time point between diagnosis of current breast cancer and randomisation. Screening bone scan is required if ALP and/or corrected calcium level are above the institutional upper limit. (Note: PET/CT scan may be used as an alternative imaging technique).

9. Serum or plasma creatinine $\leq 1.5 \times$ ULN
10. ECOG performance status 0-1
- 11A. Women who are not postmenopausal or have not undergone a hysterectomy must have documented negative pregnancy test within 28 days prior to randomisation.

Postmenopausal is defined as one or more of the following:

- Age ≥ 60 yrs
- Age < 60 and amenorrheic for 1 year or more in the absence of chemotherapy and/or hormonal treatment
- Follicle stimulating hormone (FSH) and plasma estradiol levels in the postmenopausal range for women under 60
- Radiation-induced oophorectomy with last menses > 1 year ago
- Bilateral oophorectomy

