5.5.2 Doses and treatment regimens

5.5.2.1 Olaparib and matching placebo (study treatment)

The planned dose of 300 mg b.i.d. (twice daily) will be made up of two (2) x 150 mg tablets b.i.d. (twice daily) with 100 mg tablets used to manage dose reductions as explained in [Table 5](#).

Table 5 Study treatment doses and treatment regimens

Total daily dose	Dose twice daily (b.i.d.)	Morning		Evening	
		Number of tablets	Tablet strength	Number of tablets	Tablet strength
600 mg	300 mg	2 tablets	150 mg	2 tablets	150 mg
Initial dose (300 mg twice daily) can be reduced as follows for AEs (no re-escalation allowed):					
500 mg	250 mg	1 tablet	150 mg	1 tablet	150 mg
		1 tablet	100 mg	1 tablet	100 mg
400 mg	200 mg	2 tablets	100 mg	2 tablets	100 mg
Temporary dose levels due to CYP3A inhibitor exposure (re-escalation allowed):					
300 mg	150 mg	1 tablet	150 mg	1 tablet	150 mg
200 mg	100 mg	1 tablet	100 mg	1 tablet	100 mg

As soon as possible following randomisation, patients will be administered olaparib or matching placebo orally twice daily (b.i.d.) at 300 mg for 52 weeks. Two (2) x 150 mg olaparib or matching placebo tablets should be taken at the same time each morning and evening of each day, approximately 12 hours apart with approximately 240 mL of water. The olaparib/placebo tablets should be swallowed whole and not chewed, crushed, dissolved or divided. Olaparib/placebo tablets can be taken with a light meal/snack (e.g., two pieces of toast or two biscuits).

If vomiting occurs shortly after the study treatment tablets are swallowed, the dose should only be replaced if all of the intact tablets can be seen and counted. Should any patient enrolled on the study miss a scheduled dose for whatever reason (e.g., as a result of forgetting to take the tablets or vomiting), the patient will be allowed to take the scheduled dose up to a maximum of 2 hours after that scheduled dose time. If greater than 2 hours after the scheduled dose time, the missed dose is not to be taken and the patient should take their next allotted dose at the next scheduled time. Patients should not take two doses (4 tablets) at the same time.

Within this study, patients will not be provided olaparib post discontinuation of study treatment. Patients and investigators will not be routinely unblinded to study treatment prior to the final overall survival (OS) analysis.

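### Section 5.5.12.3 relies on an entry threshold for creatinine clearance (>51 ml/min) that the eligibility criteria do not contain, so a patient already at 31–50 ml/min can be enrolled and started at 300 mg b.i.d.

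*Protocol*

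**What the plan says.** - **Section 5.5.12.3** asks for a retest if, after entry and on therapy, a patient's "estimated creatinine clearance falls below the threshold for study inclusion (>51 ml/min), retesting should be performed promptly". It continues: "A dose reduction is recommended for patients who develop moderate renal impairment", meaning a calculated clearance of 31 to 50 ml/min, with a reduced dose of 200 mg b.i.d. For that band it adds that "the investigator should use his or her discretion in determining whether a dose change or discontinuation of therapy is warranted". It recommends stopping treatment for "severe renal impairment (creatinine clearance <30 ml/min" or end-stage disease.
- **Section 4.1, criterion 9** is the only numeric renal criterion. It reads "Serum or plasma creatinine" at most 1.5 × ULN. Neither Section 4.1 nor Section 4.2 mentions clearance. Exclusions 12 (persistent toxicity of earlier cancer therapy) and 15 (poor medical risk) set no clearance limit.
- **Section 5.5.2.1** gives one starting dose: "patients will be administered olaparib or matching placebo orally twice daily (b.i.d.) at 300 mg for 52 weeks". Table 6 lists 300 mg as the starting dose, with no baseline renal adjustment.
- **Table 8** (Section 5.5.12.2) is titled "Dose reduction for study treatment to manage moderate renal impairment". It maps an initial 300 mg b.i.d. to 200 mg b.i.d. at 31–50 ml/min and does not say that the impairment must be new.
- **Section 6.2.1 and Section 6.4.11.3** list the screening procedures and the chemistry panel. The panel includes creatinine; neither list includes clearance.
- **Table 2, footnote c**: "Safety bloods samples are to be collected every 2 weeks during the first 4 weeks, then every 4 weeks until week 24", then at weeks 38 and 52.

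**The concern.** A dosing rule cites an entry criterion that the eligibility section lacks. An investigator who reads Section 5.5.12.3 could reasonably assume that everyone on study was screened to above 51 ml/min. If criterion 9 does not guarantee that, some patients enter in the range where the protocol itself recommends a lower dose. The retest trigger (clearance that falls) and the reduction text (impairment that develops) do not fit someone who was already there at baseline.

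At stake is starting exposure in those patients: 300 mg b.i.d. is 300/200 = 1.5 times the dose recommended when the same clearance arises later.

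**Working it through.** **Step 1: look for the cited threshold.** Reading every criterion in Sections 4.1 and 4.2 against Section 5.5.12.3 finds creatinine ≤1.5 × ULN and no clearance value. The figure of >51 ml/min cannot be reproduced from the eligibility text.

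**Step 2: test whether criterion 9 implies it.** Section 5.5.12.3 names Cockcroft-Gault. For a woman:

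CrCl = (140 − age) × weight × 0.85 / (72 × creatinine in mg/dL), with creatinine = m × ULN.

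The protocol gives no ages, weights or ULN values for this purpose, so all three are assumptions. Examples at ULN 1.0 mg/dL:

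- Age 65, 60 kg, m = 1.5: 75 × 60 × 0.85 / (72 × 1.5) = 3825/108 = 35.4 ml/min. At m = 1.25 it is 42.5, and at m = 1.0 it is 53.1.
- Age 55, 65 kg, m = 1.5: 43.5 ml/min.
- Age 45, 65 kg, m = 1.5: 48.6 ml/min.
- Age 70, 55 kg, m = 1.0: 45.5 ml/min.

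All of these meet criterion 9.

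**Step 3: how widely the range is reached.** The wide grid takes ages 35, 45, 55, 65; weights 50, 60, 70, 80 kg; ULN 0.9, 1.0, 1.1, 1.2 mg/dL (64 combinations).

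| Creatinine | <30 | 30 to <31 | 31–50 | >50 to 51 | >51 |
|---|---|---|---|---|---|
| 1.5 × ULN | 5 | 1 | 41 | 0 | 17 |
| 1.25 × ULN | 1 | 0 | 29 | 0 | 34 |
| 1.0 × ULN | 0 | 0 | 9 | 3 | 52 |
| 0.8 × ULN | 0 | 0 | 1 | 1 | 62 |

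The narrower grid takes ages 35, 45, 55; weights 60, 70, 80 kg; ULN 0.9, 1.0, 1.1 (27 combinations). Here 12, 3, 0 and 0 fall at 31–50 ml/min for the same four multiples, and none falls below 31.

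**Step 4: the creatinine at which the band begins.** Clearance equals 50 ml/min at creatinine = (140 − age) × weight × 0.85 / 3600. At 60 kg this is 1.35 mg/dL (age 45), 1.20 (age 55) and 1.06 (age 65). The criterion 9 ceiling over the assumed ULN range runs from 1.5 × 0.9 = 1.35 to 1.5 × 1.2 = 1.80 mg/dL. The gap is therefore reached mainly when creatinine is above ULN, or in lighter or older patients.

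**Step 5: how the bands meet.** The text uses >51 (entry), 31–50 (moderate) and <30 (severe). A value between 50 and 51 is below the entry threshold, so it is sent to retesting. A value from 30 to below 31 falls in no band.

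**The case against.** The mismatch itself is hard to dispute; the case on the other side concerns its weight.

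- **The protocol does not forbid 300 mg b.i.d. at 31–50 ml/min.** A reader might infer that such a patient is being overdosed against a firm rule. The reduction is only recommended, and the same section leaves the decision to the investigator. This stands.
- **Protection exists early.** Table 8 does not require new onset. Creatinine is available on Day 1 (or within 7 days before randomisation), at weeks 2 and 4, and every 4 weeks to week 24, and the haematological dose rules in Table 7 are mandatory. This stands as mitigation, but nothing requires clearance to be calculated before dosing, and discretion operates only once clearance is known.
- **Randomisation is 1:1**, so about half of any affected patients receive no olaparib. This stands.
- **The grid is unweighted and assumed.** A reader might take 41 of 64 as the share of patients affected. It is not: it places every patient at the criterion 9 ceiling. At ULN the count is 9 of 64 on the wide grid and 0 of 27 on the narrow one. The counts show only that the range can be reached.
- **Values between 50 and 51 ml/min** might be read as unassigned. They are not, since Section 5.5.12.3 calls for retesting. Only the gap from 30 to 31 is real, and it is a rounding matter.

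**Conclusion.** The point holds as an internal inconsistency. Section 5.5.12.3 rests on an inclusion threshold that does not exist, and criterion 9 does not supply it. A patient at 31–50 ml/min, or less often below 30, can be enrolled and started at 300 mg b.i.d. without any required clearance calculation.

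That such patients can qualify rests on the Cockcroft-Gault formula with assumed ages, weights and ULN values. How many there are cannot be derived from the protocol; the number is probably small.

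A reader might infer a threat to the trial's conclusions. The document does not support that: this is a dosing-safety matter, and power, alpha and the primary IDFS analysis are unaffected. Severity is minor to should-fix.

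**What to change.** **Patients still to be enrolled.** Add calculated creatinine clearance >51 ml/min (Cockcroft-Gault or 24-hour urine) to criterion 9, using the figure Section 5.5.12.3 already states. Table 16 shows 1299 of 1800 randomised by February 2018, so this reaches at most 1800 − 1299 = 501 patients (27.8%) across both protocol versions.

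**Patients on treatment.** Calculate clearance from data already collected. Apply Table 8 and the discretion paragraph of Section 5.5.12.3 whether the impairment was present at entry or developed later, and say so in that section.

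**Optional.** Close the gap from 30 to 31 ml/min by stating that clearance is rounded to whole numbers and placing 30 in the moderate band, in both Section 5.5.12.3 and Table 8.

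**Rest of the World version.** The synopsis describes it as identical in scientific content, but it is not at hand. Make the same correction there if it has the same text.

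**Cost.** One line in criterion 9, one paragraph in Section 5.5.12.3 and, if the rounding gap is closed, an edit to Table 8. Date of birth, weight and creatinine are already collected at screening, so no new test is needed. A few otherwise eligible patients would be excluded. A patient reduced to 200 mg b.i.d. is at the lowest adverse-event dose level, so no further step remains and re-escalation is barred; the site must also request 200 mg kits under Section 5.5.6.

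An alternative is to delete the reference to an inclusion threshold and define a 200 mg b.i.d. starting dose for baseline clearance of 31–50 ml/min. That avoids excluding patients in that band but would need a 200 mg starting supply.
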